Recently, Alcon introduced VERION™ Image Guided System: Digital Surgical Planning and Positioning Tools. This system encompasses a reference unit that takes a picture of the eye with the patient in the sitting position creating a high-resolution digital image of the patient's eye, capturing scleral vessels, limbus and iris features. It measures keratometry as well as the corneal diameter (limbus) and pupil size. The information captured is then transferred automatically to the planner where additional information including target refraction, manifest refraction, axial length, anterior chamber depth, and lens thickness is entered for IOL power calculation and astigmatism correction planning. Astigmatism correction options include corneal incisions, toric IOL and a combination of both. Intraoperatively, The VERION™ Digital Marker displays patient information and images from the VERION™ Reference Unit. Additionally it positions all incision locations and assists with lens alignment in real time while accounting for the variable impact of cyclorotation and patient eye movement. In the OR, it displays a reticle that helps to align the IOL to the axis according the surgical plan.c It also helps to position manual LRIs.

Additionally, intraoperative wavefront aberrometry has been used in the last couple of years with increase success. The Optiwave Refractive Analysis (ORA) system can refract the eye in phakic, aphakic, and pseudophakic states at any time during cataract surgery and assists in IOL power selection and recommendations for toric IOL positioning before and after implantation as well as LRIs confirming the surgery plan calculated preoperatively. Furthermore, VerifEye, an ORA hardware upgrade, provides continuous assessment of the patient's eye allowing for more precise measurements; therefore, more accurate results and improved refractive outcomes and VerifEye +, the latest upgrade that provides streaming information on the refractive status and correct IOL positioning through the right ocular of the surgical microscope. This enables the surgeon to visualize all the information without having to look up at the monitor screen during the surgical procedure.

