## **OBJECTIVES:**

The main objective of this study is to evaluate spherical and astigmatism outcomes post routine cataract surgery when the complete VERION™ Image Guided System packet + ORA System with VerifEye or VerifEye + are used in the treatment of pre-existing astigmatism using toric intraocular lens (IOL) or corneal incisions compared to the surgeon's standard of care.

Exploratory objective is to evaluate the LRI enhancement feature of the ORA System with VerifEye or VerifEye + in subjects undergoing standard IOL implantation and corneal incisions.

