**b. Measurements and evaluations**

1. Visit 1: Informed consent process will be conducted at this visit. Assessments include uncorrected and best-corrected ETDRS visual acuity (UCVA / BCVA), manifest refraction, intraocular pressure (IOP), and slit lamp examination including dilated fundus exam, auto refractor keratometry, Lenstar, VERION™ Reference Unit, and corneal topography (Atlas). Both IOL power and astigmatism correction will be calculated using the surgeon's current standard of care as well as using the VERION™ Image Guided System: Digital Surgical Planning. Any testing that is part of the site's standard of care preoperative cataract surgery evaluation may be performed prior to the informed consent being signed provided these tests are conducted within 90 days of the surgery and notation of the date performed is entered onto the source document.

The first eye undergoing surgery will be randomized to either one of the two groups: Group A (surgeon standard of care) or B (VERION™ Image Guided System + ORA System with VerifEye or VerifEye +). The fellow eye will be assigned to the alternate group. Eyes will be randomized after all calculations have been completed. Prior to randomization, all measurements, IOL power and astigmatism correction calculations will be reviewed following the practice standard of care to determine subject's eligibility for astigmatism correction with toric lens or corneal incisions. If it is determined that the measurements are not consistent then subject will be excluded from the study.

The surgeon's standard pre cataract surgery treatment will be used in all his patients.

2. Visit 2: The surgeon may use his preferred cataract extraction technique (manual or laser) for eyes randomized to Group A. Eyes randomized to Group B will undergo laser assisted phacoemulsification (primary incision, capsulorhexis and lens fragmentation) using the surgeon's preferred laser settings. The secondary incision will be made with the laser or manually, at the surgeon's discretion. The lens will be implanted in the bag. The surgeon's standard post cataract surgery treatment will be used in all his patients.
3. Visit 3: Assessment will include uncorrected ETDRS visual acuity, intraocular pressure, slit lamp examination, corneal incision location and/or toric IOL orientation.

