#### **SAMPLE SIZE**

Sample size calculations are based on a presumed t-test of refractive cylinder and corneal astigmatism between the two study groups. An alpha of 0.05 and a power of 0.8 were used. The standard deviations of the variables above have been previously estimated at about 0.35D. A difference of 0.25D would be clinically relevant. Using the information above, to reliably detect a difference between groups would require 34 eyes in each group. Spherical equivalent refraction, corneal astigmatism and refractive cylinder are likely to be highly correlated. Allowing for multiplicity of results, approximately 10% more eyes are required per additional correlated endpoint. In this case, 20% more eyes would be required, for a total of 40 eyes (20 subjects) per group.

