#### **STATISTICAL CONSIDERATIONS**

All data will be collected by the research team. Data will be entered into a database. The database will be password protected and access will be restricted to study personnel. Data analysis will be performed without patient identification. Statistical analysis will be done using standard descriptive statistics and other tests as deemed appropriate based on the characteristics of the data to be analyzed. Secondary endpoints will be analyzed only if the primary endpoint demonstrates a statistically significant difference between groups. Corneal and refractive astigmatism are likely to be correlated. A Bonferroni correction will be applied where indicated for evaluating significance. Mean spherical equivalent refraction is not expected to be highly correlated to the measured astigmatism, nor is mean keratometry, so multiplicity considerations will not be required for these variables. All statistical tests will be two-sided and interpreted at a 5% significance level. Comparisons between the two groups will be made. Data analysis will be conducted by a third party consultant.

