**Primary Endpoint:**

- Residual refractive cylinder at 3 months

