**Secondary Endpoints:**

- Residual mean spherical equivalent refraction at 3 months
- Residual corneal astigmatism at 1 month and 3 months
- Residual refractive sphere at 1 month and 3 months
- Interim refractive cylinder at 1 month
- Percentage of eyes with postoperative MRSE accuracy to target  $\leq 0.5D$  at 1 and 3 months
- Uncorrected and best-corrected visual acuity at 1 month and 3 months
- Axis of placement (actual vs. intended)
- Lenstar K's vs. Verion K's
- Corneal incisions stability (manual vs. laser arcs) at 3 months after surgery - based on manifest cylinder and keratometry measurements from 1 and 3 months, noted above.

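### Residual corneal astigmatism is compared without separating toric from incision eyes, so toric-only eyes dilute this secondary comparison and the 0.8 power stated for it does not hold.

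*Combined protocol and SAP*

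**What the plan says.** - **Modes of correction.** The Objectives section covers "treatment of pre-existing astigmatism using toric intraocular lens (IOL) or corneal incisions". The introduction adds, of the planning system, "Astigmatism correction options include corneal incisions, toric IOL and a combination of both".
- **When the mode is considered.** Under Measurements and evaluations, Visit 1, both the standard and the VERION calculations are made and reviewed before randomization "to determine subject's eligibility for astigmatism correction with toric lens or corneal incisions".
- **Endpoints.** The primary endpoint is "Residual refractive cylinder at 3 months". The secondary list includes "Residual corneal astigmatism at 1 month and 3 months", with no restriction by type of correction. A separate secondary item concerns the stability of corneal incisions.
- **Analysis.** Statistical Considerations says "Comparisons between the two groups will be made" and leaves the choice of tests to the characteristics of the data. It gives no stratification, adjustment or subgroup by type of correction. Secondary endpoints are analyzed only if the primary is significant.
- **Sample size.** The calculation rests on a "presumed t-test of refractive cylinder and corneal astigmatism between the two study groups", with alpha 0.05, power 0.8, SD about 0.35 D and a relevant difference of 0.25 D. It arrives at 34 eyes per group, raised to 40 for multiplicity.

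**The concern.** Refractive cylinder measures what is left after either kind of correction. Corneal astigmatism does not. Corneal incisions change the cornea, while a toric lens compensates for it from inside the eye. A well-aligned and a poorly aligned toric-only eye have the same corneal cylinder, so the variable cannot register the toric planning and axis alignment that the test system is meant to improve.

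If all eyes go into one comparison, toric-only eyes contribute an expected difference of about zero and shrink any real effect in incision eyes. Two things are at stake. The Sample Size section attributes 0.8 power to a comparison that may have far less. And after a positive primary result, a null result here could be misread as saying that the system does nothing for corneal incisions.

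**Working it through.** **Inputs from the documents:** difference 0.25 D, SD 0.35 D, two-sided alpha 0.05, power 0.8, 34 eyes per group before inflation and 40 after (Sample Size; sidedness from Statistical Considerations).

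**Assumptions, not in the documents:** the share p of eyes with a toric lens and no astigmatic incision (25%, 50%, 75%); zero group effect on the cornea in those eyes; the full 0.25 D effect in incision eyes; 40 eyes in each group.

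**Step 1. The plan's own figure.** The standardized difference is 0.25 / 0.35 = 0.714. A two-sample t-test at power 0.8 needs 31.8, so 32 eyes per group, close to the stated 34. The 20% inflation gives 34 × 1.2 = 40.8, against the stated 40. With 40 eyes per group and no dilution, power is 0.88.

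**Step 2. Diluted effect.** The pooled difference is (1 − p) × 0.25 D. Incision eyes alone keep 0.25 D but number 40 × (1 − p) per group. Power is from the noncentral t distribution with SD 0.35 D.

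| Toric share p | Pooled difference (D) | Pooled power, 40 per group | Incision eyes per group | Power, incision eyes only |
|---|---|---|---|---|
| 0% | 0.25 | 0.88 | 40 | 0.88 |
| 25% | 0.1875 | 0.66 | 30 | 0.78 |
| 50% | 0.125 | 0.35 | 20 | 0.60 |
| 75% | 0.0625 | 0.12 | 10 | 0.33 |

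**Step 3. Eyes needed for 0.8 power when pooled.** By the normal approximation, n = 2 × (1.96 + 0.84)² × 0.35² / difference², which gives 55, 124 and 493 eyes per group at the three shares.

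**Step 4. Spread.** Step 2 holds the SD at 0.35 D. If toric eyes also keep on average 1.0 D more corneal cylinder than incision eyes (assumed), the unpaired SD at p = 50% is √(0.35² + 0.5 × 0.5 × 1.0²) = 0.61 D, and pooled power falls from 0.35 to 0.15.

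**Step 5. Pairing.** The design is contralateral, so a paired test is natural. With an assumed within-subject correlation of 0.5, the SD of the difference is 0.35 × √(2 × 0.5) = 0.35 D. With 40 pairs, pooled power is 0.91, 0.60 and 0.20. Adding the variance p(1 − p) × 0.25² that arises because the effect differs by mode gives 0.88, 0.55 and 0.18. Pairs with both eyes planned for incisions give 0.97, 0.86 and 0.52, but only if every subject has the same mode in both eyes. If modes were independent between eyes, 40 × (1 − p)² pairs would remain, about 22, 10 and 2 to 3, with power of about 0.89, 0.52 and at most 0.12. Pairing softens the dilution but does not remove it. The paired figures also depend on a correlation and a same-mode proportion that the documents do not give.

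**The case against.** The strongest reply concerns consequence. The endpoint is one of nine secondary items and is tested only after a significant result on refractive cylinder, which captures both modes of correction. A reader might infer that the trial's main conclusion or its sample size is at risk. The documents do not support that: the primary endpoint is untouched, and the same difference and SD size the trial for refractive cylinder. A null corneal result could arise only after benefit had been shown on the all-eyes measure. This stands and limits the point to a secondary analysis.

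A reader might also infer that the plan prescribes pooling. It does not say so. It leaves the analysis set unspecified, and pooling is the default reading. The incision-stability item is specific to incisions, but it measures change over time and does not replace this comparison.

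Nor do the documents support saying that no toric eye can show a corneal difference. Eyes with a toric lens plus incisions can change at the cornea. The primary incision is made by laser in Group B and by the surgeon's choice of technique in Group A, so corneal change could differ even in toric-only eyes, though that would not be toric benefit. The gain from restriction depends on a near-zero effect in eyes counted as toric. In the two-sample model, pooling does as well as restriction once those eyes carry about 45%, 40% or 31% of the incision-eye effect (0.11, 0.10 or 0.08 D) at the three shares.

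Finally, the magnitudes are conditional. The stated 40 eyes and 20 subjects per group are ambiguous in a contralateral design. With 20 eyes per group, incision-only two-sample power is 0.47, 0.33 and 0.17. With 40 per group and a Bonferroni alpha of 0.025, it is 0.68, 0.48 and 0.23. So restriction does not rescue the power claim. It makes the comparison interpretable.

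**Conclusion.** The point holds for toric-only eyes and for the power claim. As written, the comparison mixes eyes in which the variable can respond to the planned correction with eyes in which it cannot, and the 0.8 power stated for corneal astigmatism requires essentially no dilution. At 40 eyes per group, pooled two-sample power falls from 0.88 to about 0.66, 0.35 or 0.12 at toric shares of 25%, 50% or 75%. Incision eyes alone give 0.78, 0.60 or 0.33. These figures rest on an assumed toric share, zero effect in toric-only eyes, an unchanged SD and 40 eyes per group. The direction is secure; the size is not known from the documents. This should be changed, but it does not threaten the primary conclusion.

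**What to change.** 1. At the pre-randomization review, record the planned correction type for each eye: incisions only, toric only, or both. State which plan defines the type if the standard and VERION plans differ. The review currently addresses the subject's eligibility and does not clearly fix a type per eye. Recording it then keeps the subset a baseline one.
2. Make the between-group comparison of corneal astigmatism in pairs with both eyes planned for corneal incisions without a toric lens. Report toric-only, combined and mixed-mode pairs descriptively by type.
3. In Sample Size, restate the power claim as applying to refractive cylinder only.

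The cost is one recorded item and a few sentences, with no new visits or measurements. The downside is fewer eyes in this secondary analysis. It may then be underpowered and should be presented as such.

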**Safety Analyses**

The type, severity, duration and frequency of reported ocular adverse events will be tabulated for each group. Adverse events will also be summarized for events that were considered treatment-related. Comparison of treatment groups with respect to the proportion of study patients reporting adverse events will be made using a chi-square test.

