4. Visit 4 and 5: Assessment will include uncorrected and best-corrected ETDRS visual acuity (UCVA / BCVA), manifest refraction, auto refractor keratometry, Lenstar, VERION™ Reference Unit, corneal topography, intraocular pressure, and slit lamp examination. The location of all corneal incisions as well as toric IOL orientation will be documented.

Adverse events and device deficiencies/quality complaints will be monitored and recorded at all study visits.

**Table 1.** Visits and Study Assessments

Study Assessments	Visit 1 Preoperative	Visit 2 Operative	Visit 3 Day 1	Visit 4 Day 20-40	Visit 5 Day 75-105
Inclusion/Exclusion Criteria	x				
Consent Subject	x				
Patient demographics (age, gender, race, ethnicity)	x				
Manifest Refraction	x			x	x
UCDVA	x		x	x	x
BCDVA	x			x	x
Tonometry (IOP)	x		x	x	x
Complete slit lamp exam	x		x	x	x
Dilated fundus exam	x			†	†
Auto refractor keratometry	x			x	x
Atlas corneal topography	x			x	x
Lenstar LS900 measurements	x			x	x
Verion™ Reference Unit measurements	x			x	x
Verion™ Planner	x				
Alcon Toric calculator	x				
LRI calculator	x				
Incision Size and Location		x			
Record Lens Model Implanted (Attach label, or record manufacturer, model, power)		x			

VerifEye or VerifEye + information		x			
Post-IOL implantation incision size		x			
LenSx parameters		x			
Corneal arcs/toric IOL orientation		x	x	x	x
Adverse events / device deficiency	x	x	x	x	x

x To be performed as scheduled

† To be performed as deemed necessary by the investigator.

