## ADVERSE EVENTS AND DEVIATION REPORTING

All efforts will be made to look for possible adverse events or untoward findings. If an adverse event occurs, the safety and welfare of the subject will be the priority. Appropriate medical intervention will be made. Ocular adverse events observed by the investigator or reported by the subject, and in the investigator's opinion to be directly related to any of the devices being evaluated, will be recorded on an Adverse Event Case Report Form. Resolution of the adverse event will be recorded on the Adverse Event Follow-Up Form.

This is an Investigator Initiated Trial; however, notification of a serious ocular adverse event directly related to the evaluated devices will be made to the device manufacturer within 24 hours. Carolina Eyecare Physicians will support the manufacturer in the following-up of all events so that complete information is available to maintain patient safety and for them to comply with the appropriate regulatory reporting requirements.

Adverse events and deviations will be reported to the IRB following the IRB's Reporting Guidelines for Unanticipated Problems, Deviations, and Other Safety Information.

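### Measured best-corrected acuity is a gated secondary endpoint, so a non-significant primary removes its only planned by-group analysis, and the ungated safety analysis covers reported adverse events only

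*Combined protocol and SAP*

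**What the plan says.** The Safety Analyses section has three elements: a tabulation ("The type, severity, duration and frequency of reported ocular adverse events will be tabulated for each group"), a summary of the events considered treatment-related, and one test ("Comparison of treatment groups with respect to the proportion of study patients reporting adverse events will be made using a chi-square test"). It names no measured variable.

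The Secondary Endpoints list includes "Uncorrected and best-corrected visual acuity at 1 month and 3 months". The primary endpoint is "Residual refractive cylinder at 3 months". Statistical Considerations links the two: "Secondary endpoints will be analyzed only if the primary endpoint demonstrates a statistically significant difference between groups". No section exempts acuity from this rule.

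Section 6.b and Table 1 schedule best-corrected acuity at Visits 1, 4 and 5, and intraocular pressure and slit lamp at Visits 1, 3, 4 and 5. For Day 1 the text reads "Assessment will include uncorrected ETDRS visual acuity, intraocular pressure, slit lamp examination, corneal incision location and/or toric IOL orientation". For Visits 4 and 5 the list ends with "corneal topography, intraocular pressure, and slit lamp examination". Neither pressure nor slit-lamp findings appear under Study Endpoints or Safety Analyses.

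Adverse Events and Deviation Reporting states which ocular events go on the form: those that in the investigator's opinion are "directly related to any of the devices being evaluated, will be recorded on an Adverse Event Case Report Form".

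**The concern.** Best-corrected acuity shows whether an eye sees as well as it can once refractive error is removed, so it bears on surgical harm as well as on benefit. The plan treats it only as a follow-on to an efficacy result. A trial that finds no gain in cylinder is the one in which a reader most needs to know whether the new pathway cost any vision, and in that case the plan provides no analysis of it.

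A difference between groups is not far-fetched. Under section 6.b, Group B eyes must have laser-assisted phacoemulsification, while Group A eyes may have manual or laser extraction. The groups therefore differ in surgical technique as well as in planning and alignment.

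The adverse event route is a partial substitute at best. It depends on an attribution to the devices under evaluation, and a Group A eye treated with ink marks and manual incisions has little exposure to them. Measured acuity and pressure do not depend on that judgement.

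**Working it through.** **1. Where each measurement is analysed**

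| Measurement | Collected after surgery | Planned by-group analysis | If the primary is not significant |
|---|---|---|---|
| Reported ocular adverse events | All visits | Safety Analyses | Still done |
| Best-corrected acuity | Visits 4, 5 | Secondary endpoint only | Not done |
| Intraocular pressure | Visits 3, 4, 5 | None named | None named |
| Slit-lamp findings | Visits 3, 4, 5 | None named | None named |

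**2. The plan's own sample size.** Inputs from Sample Size: difference 0.25 D, SD 0.35 D, alpha 0.05 (two-sided, from Statistical Considerations), power 0.80.

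- Standardised difference: 0.25 / 0.35 = 0.714.
- Normal approximation: n = 2 × (1.96 + 0.84)² / 0.714², about 31 per group.
- Noncentral t: 31.8, so 32 per group. The plan states 34, which this reproduces to within 2 eyes.
- 20% increase: 34 × 1.2 = 40.8, against the stated 40.

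**3. How often the gate stays closed.** P(closed) = 1 − P(primary significant).

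- No true difference: 1 − 0.05 = 95%.
- Stated power: 1 − 0.80 = 20%.

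Sample Size gives 40 eyes (20 subjects) per group. Each subject contributes one eye to each group, so 20 subjects give 20 eyes per group and 40 eyes per group need 40 subjects. Both are shown, with the 34 before inflation, for an independent-groups t-test:

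| True difference | Eyes per group | Power | Gate closed |
|---|---|---|---|
| 0.25 D | 40 | 0.884 | 12% |
| 0.25 D | 34 | 0.827 | 17% |
| 0.25 D | 20 | 0.595 | 40% |
| 0.125 D | 40 | 0.351 | 65% |

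The design is contralateral, so a paired test is natural, but the plan gives no between-eye correlation. Taking the correlation ρ as an assumption, the SD of the within-subject difference is 0.35 × √(2(1 − ρ)). For 20 pairs and a true difference of 0.25 D:

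| Assumed ρ | Power | Gate closed |
|---|---|---|
| 0 | 0.573 | 43% |
| 0.3 | 0.726 | 27% |
| 0.5 | 0.858 | 14% |
| 0.7 | 0.974 | 3% |

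The figure at the design difference therefore runs from 3% to 43%, depending on facts that the plan does not settle. The 95% under no difference does not depend on them.

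**The case against.** The best counter-argument is that the gap is narrower than it looks. A reader might infer that a null primary leaves no by-group look at vision loss at all. The documents do not support that. A loss of vision, a pressure rise or a corneal finding recorded as an adverse event is tabulated by group with no gate. Section 6.b has adverse events monitored and recorded at every visit, and the separate summary of treatment-related events suggests that the tabulated set may be wider than those events. This stands, subject to the relatedness wording in the reporting section, which the plan does not reconcile with these statements.

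A reader might also infer that pressure and slit-lamp data can never be compared. Nothing bars it. Statistical Considerations allows descriptive statistics and group comparisons in general terms, and Confidentiality/Publication allows further analysis depending on the results. On its own, this part is close to missing detail. But the general sentences name no safety variable, and an analysis chosen after seeing the results does not replace a planned one.

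The gate sentence sits among statements on multiplicity, so it could be meant to limit formal testing and leave descriptive summaries free. That is a reasonable intention, but the sentence restricts analysis without qualification.

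Finally, the documents do not call best-corrected acuity a safety measure, and its place in the list is a choice, not a contradiction. That is true. The point is what the gate does to it.

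**Conclusion.** The point holds for planned analyses of measured acuity. Followed literally, the plan drops the by-group analysis of best-corrected acuity whenever residual cylinder is not significant. Here a stated rule produces the gap; it is not a matter of omitted detail. The lack of a planned summary for pressure and slit-lamp findings is a lesser, related gap that applies whatever the primary shows.

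The 20% is only one minus nominal power and should not be read as a precise forecast. These probabilities describe how often the analysis is withheld; they say nothing about how likely or how large any missed harm would be. The conclusion assumes that the gate means what it says and that no separate analysis document exempts acuity. The primary analysis is unaffected. The change is worth making because it costs little.

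**What to change.** In Statistical Considerations and Safety Analyses, state that best-corrected acuity is reported as a safety measure whatever the primary result:

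- The main summary is the within-subject difference (Group B eye minus Group A eye) in acuity at Visit 4 and at Visit 5, with 95% confidence intervals.
- Alongside it, give change from Visit 1. Change alone is not enough: cataract lowers preoperative acuity, so an eye harmed by surgery can still show a gain.
- Give the number of eyes per group below an acuity level, or with a loss, that the investigators fix in advance. A count of any loss without a threshold would be hard to interpret.
- Include every operated eye with available data. Section 3.c removes subjects with stated surgical complications or aborted surgery, the latter also from the efficacy analysis, and section 7.c terminates those with possibly related severe events. Such eyes may lack Visit 4 or 5 values, so report how many are missing, by group and reason. The within-subject difference needs both eyes, but the per-group tables do not.

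Add by-group descriptive tables of intraocular pressure and slit-lamp findings at Visits 3, 4 and 5. Reconcile the adverse event recording rule with the statement that events are recorded at all visits, so that the tabulated set is clear. Keep uncorrected acuity as a gated efficacy endpoint.

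The cost is a few descriptive tables from assessments already scheduled, with no new visits or procedures and no change to alpha or sample size.

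### Adverse events are compared by an unpaired 5% chi-square test with no interval, although each patient is in both groups and, if event rates are low, the test has little power

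*Combined protocol and SAP*

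**What the plan says.** Safety Analyses opens with description: "The type, severity, duration and frequency of reported ocular adverse events will be tabulated for each group". It adds a summary of events considered treatment-related, and then names one inferential comparison: "Comparison of treatment groups with respect to the proportion of study patients reporting adverse events will be made using a chi-square test". Statistical Considerations sets the rule for reading it: "All statistical tests will be two-sided and interpreted at a 5% significance level".

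Neither section plans a risk difference, a confidence interval or a margin for adverse events, and the documents give no expected event rate. The Sample Size section concerns efficacy only: "Sample size calculations are based on a presumed t-test of refractive cylinder and corneal astigmatism between the two study groups". It arrives at 34 eyes per group, raised to 40, with 20 subjects given in brackets.

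Two other places bear on the point. Under Measurements and evaluations, Visit 1, the first eye is randomised and the fellow eye goes to the other group, so every patient contributes one eye to each. Under Adverse Events and Deviation Reporting, the adverse event form is for ocular events that the investigator judges directly related to the devices.

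**The concern.** The groups differ in surgical exposure. Laser-assisted phacoemulsification is specified for Group B and optional for Group A, and Group B adds the VERION and ORA steps. Publication is planned, so a reader is likely to look for a by-group statement on harm.

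Two features make the planned test a poor basis for one. First, it treats the groups as independent samples of patients when they are the two eyes of the same patients. Second, a p-value read at 5% does not show how large an excess of events the data leave open. In a trial not sized for adverse events, that is the useful information. If events are uncommon, a non-significant p-value is the likely result even when one group truly has more of them.

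**Working it through.** **Inputs.** From the documents: two-sided 5% level; 40 eyes per group, or 20 if the bracketed 20 subjects is the total in a contralateral design. Both sizes are used because the documents do not settle which is meant. Assumed, because the documents give none: control event rates from 2% to 20%, doubled or tripled in the other group.

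**1. The plan's own sample size.** The inputs are "An alpha of 0.05 and a power of 0.8 were used", an SD of 0.35 D and a difference of 0.25 D. The normal approximation gives n = 2 × (1.960 + 0.842)² × (0.35/0.25)² = 2 × 7.85 × 1.96 = 30.8, so 31 per group. The noncentral t calculation gives 32, and the stated 34 has power 0.827. Then 34 × 1.2 = 40.8, against the stated 40. The figure is reproduced to within about two eyes, and no adverse-event quantity enters it.

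**2. How often the chi-square test misses.** With x and y events in two groups of n eyes, the uncorrected statistic is X² = 2n(y − x)² / [(x + y)(2n − x − y)], significant if above 3.8415. Power is the sum of the binomial probabilities of all (x, y) that reject, treating the groups as independent. The miss rate is 1 minus power:

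| True rates | Missed, 40 eyes per group | Missed, 20 eyes per group |
|---|---|---|
| 2% v 4% | 96% | 99.5% |
| 2% v 6% | 89% | 98% |
| 5% v 10% | 85% | 95% |
| 5% v 15% | 65% | 85% |
| 10% v 20% | 75% | 86% |
| 10% v 30% | 37% | 64% |
| 15% v 45% | 15% | 43% |
| 20% v 60% | 3% | 25% |

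A doubling is missed more than half the time when the control rate is below about 20% (40 eyes) or 32% (20 eyes). For a tripling the limits are about 8% and 13%.

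**3. Checks that need no assumed rate.**
- 0 v 3 events in 40 eyes each: X² = 80 × 9 / (3 × 77) = 3.12, not significant.
- 0 v 3 events in 20 eyes each: X² = 40 × 9 / (3 × 37) = 3.24, not significant.
- 0 v 4 events in 40 eyes each: X² = 80 × 16 / (4 × 76) = 4.21, significant.
- No events at all: the exact two-sided 95% upper limit is 1 − 0.025^(1/n), which is 8.8% for 40 eyes and 16.8% for 20.

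**4. Does a paired test cure the low power?** Exact McNemar, 40 pairs, within-patient correlation (phi) from 0 to 0.4:
- 5% v 10%: misses 96% to 97%.
- 10% v 20%: misses 85% at phi 0, falling to 81% at 0.4.
- 10% v 30%: misses 50% at phi 0, falling to 27% at 0.4.

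Pairing is needed for validity, but at low rates it does not restore power.

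**5. What an interval would show.** Illustrative Newcombe 95% intervals, computed as for independent groups:
- 2 v 2 events in 40 eyes each: difference 0, from −12 to +12 percentage points.
- 4 v 8 events in 40 eyes each: +10, from −6 to +26.
- 2 v 2 events in 20 eyes each: 0, from −21 to +21.

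**The case against.** The strongest reply is that the plan claims nothing about equal safety. The hypothesis, objectives and endpoints concern refractive outcomes, with no safety equivalence or non-inferiority claim. A reader might infer that a non-significant test will be taken as equal safety, but no section says so. That stands: the misreading is a risk the plan leaves open, not a conclusion it draws.

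A reader might also infer that the chi-square is the only safety result the plan can give. It is not. The by-group tables are also planned, and anyone could derive a difference from them. What stands is that no interval is committed to and that the one named inferential method is unpaired.

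The power figures rest on assumed rates. A flat statement that a tripling is usually missed would be wrong: at 10% v 30% with 40 eyes per group it is detected 63% of the time, and at 15% v 45% 85% of the time. No safety power is planned either, so the 0.8 in Sample Size is not a standard this test was meant to meet. Nor does a paired test always miss more often: at 10% v 30%, 40 pairs and phi 0.4, exact McNemar misses 27% against 37% for the chi-square.

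Finally, low power for adverse events is usual in a small trial sized on efficacy, and an interval covers only the events that are recorded. Both are true. Neither defends an unpaired test on patients who are in both groups.

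**Conclusion.** The point holds in a limited, conditional form. The planned between-group safety comparison consists of descriptive tables and one unpaired chi-square test read at 5%, with no interval, in a design where every patient has an eye in each group. That much follows from the text alone.

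The claim of low power depends on the event rate, which the documents do not give. Restricting the form to device-related ocular events makes low rates plausible but fixes no number. For control rates of 5% to 10% and 40 eyes per group, a doubling is missed 75% to 85% of the time and a tripling 37% to 65%; with 20 eyes per group the ranges are 86% to 95% and 64% to 85%. These figures treat the eyes as independent and indicate scale only.

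The documents do not support saying that the trial will report equal safety, or that large increases would be missed whatever the base rate. No refractive or visual conclusion is affected.

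**What to change.** In Safety Analyses:
- Make the eye the unit. For each group, give the number and percentage of eyes with at least one ocular adverse event, with an exact 95% interval.
- Replace the chi-square test with the paired Group B minus Group A risk difference, (b − c)/n, and a 95% confidence interval for paired proportions. Here b and c are the patients with an event only in the Group B eye or only in the Group A eye, and n is the number of pairs.
- State that any p-value comes from a paired test and is descriptive, and that a non-significant result will not be reported as showing equal safety.
- State that the interval covers only the events recorded under Adverse Events and Deviation Reporting, that is, ocular events judged device-related.

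In Statistical Considerations, exempt safety from the sentence that sets the 5% level. Before any power or precision is quoted, reconcile 40 eyes with 20 subjects per group in Sample Size.

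The cost is wording only: no new data, visits or subjects. The drawback is that the report shows a wide interval where it might otherwise have said simply that there was no difference.
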